### **5.2.2. Prospective data collection and analysis of HCV transmission clusters in Wisconsin.**

Remnant blood specimens from the confirmatory testing procedures collected from prospectively enrolled study participants will also be used to support the GHOST-related research aims of the multi-site collaborative research program. Upon receipt of a reactive rapid antibody detection test, Vivent Health staff will draw 5 mL of blood into each of up to 3 serum separator tubes (SST), depending on how many of the 3 rapid antibody detection tests had a reactive result.

SST tubes will be centrifuged within 2 hours at the Vivent Health prevention office, according to the Standard Operating Procedures developed between Vivent Health and the Wisconsin State Laboratory of Hygiene. After centrifugation, the SST tubes will be kept cold (4-8°C) and shipped together with the appropriate requisition forms to WSLH via overnight delivery. Confirmatory testing will be performed on specimens on the day of receipt, and aliquots of residual serum will be transferred to secondary tubes and placed in a -80°C laboratory freezer for indefinite storage.

Stored serum specimens for HIV, hepatitis C, and Syphilis positive participants will be shipped to GHOST laboratories for phylogenetic testing on a monthly basis. GHOST laboratories are housed at Massachusetts General Hospital and the CDC. They will perform genetic sequencing of the virus to understand networks. The data will then be uploaded to a secured web interface in order for researchers and the Department of Health Services to access sequence data.

Access to the sequencing data by the Wisconsin Project team will be allowed through the National Healthcare Safety Network's system, known as SAMS. The Centers for Disease Control and Prevention's (CDC) Secure Access Management Services (SAMS) is a federal information technology (IT) system that gives authorized personnel secure access to non-public CDC applications. The SAMS partner portal is a website designed to provide centralized access to public health information and computer applications operated by the CDC. For the National Healthcare Safety Network (NHSN) Program, SAMS will provide healthcare facilities and other partners, such as state health departments and QIOs, with secure and immediate access to the NHSN application.

The UW-Madison-based PI and partners at WI DHS HIV and Viral Hepatitis Program will be granted access to SAMS by CDC after completing the required NHSN training. Data accessed through SAMS will be limited to the viral sequence data derived from the coded HCV RNA-positive samples sent to the GHOST laboratory. No direct identifiers will be associated with data that is accessible through SAMS. Additional information about SAMS is available at <https://www.cdc.gov/nhsn/sams/sams-user-faq.html#a1>.

### **5.3. Data collection for Aim 2.**

Guided by the social ecologic framework (see Section 1.4), we will assess (a) community-level vulnerability to consequences of injection drug use and (b) availability of essential prevention services through data collection at the county-level, health system and provider-level, and client-level. Interview guides for clients and local service providers will be developed collaboratively by the

research team and Vivent Health staff after the SSP staff interviews have been conducted and analyzed.

**Aim 2a. County-level data.** We will map out and organize project-related resources within our designated counties. An assessment of service needs and gaps will be conducted. We will identify additional sources of county-level data to complement our preliminary compilation of data that guided the proposal, including use of PDMP and State opioid treatment authority to identify capacity to prescribe MAT and the current level of utilization. Availability of these data sources are reflected in letters of support from WI DHS collaborators.

**Aim 2b/Aims 2c. Provider- and client-level data.** Semi-structured individual elicitation interviews will be administered to obtain insight from providers of services to injection drug users and clients of these agencies about the context of opioid use and barriers and facilitators of service access and usage.

**Aim 2b. Provider interviews** will be conducted in person or by phone, and are expected to last 30-45 minutes in duration. They will be audio-recorded and transcribed for later analysis. The goals are to assess (1) services provided to opioid users, (2) barriers and facilitators of access to their services, (3) gaps in service, and (4) strategies to address these gaps. We also will assess the agency's willingness to support a community-based, client-centered prevention home approach to reducing opioid use and infectious disease transmission risk among opioid users. The provider interviews, along with the county-level resource mapping, will inform the readiness and ability of the county to implement a comprehensive prevention program. Agencies will be purposively recruited to represent multiple service domains, including HIV/HCV/STI testing and treatment, medical and mental health, substance misuse treatment, psychosocial assistance, health officials, and law enforcement. The specific provider sample size will depend on the number and variability in the county resources mapped out in Aim 2a.

**Aim 2b. Provider mail and email-based surveys.** A survey investigating willingness to screen and treat PWID for HCV and opioid use disorder will be developed in collaboration with other UG3 sites. The goals of this mail and email-based survey are to quantitatively assess (1) the willingness of rural primary care providers to provide treatment for HCV infection and/or opioid use disorder as primary prescribers, (2) the prevalence and correlates of failure to provide appropriate screening for HIV, viral hepatitis, and sexually transmitted diseases for people who inject drugs, and (3) negative provider attitudes towards people who inject drugs that may serve as a barrier to effective primary care in rural communities. A cover letter, paper survey, and a \$5 incentive will be mailed to selected providers along with materials and instructions for mailing completed surveys back to study staff at UW-Madison. To increase the response rate of the provider survey, providers who have not responded to the survey will be emailed with a web-link to the same survey.

**Aim 2c. Client interviews** will be conducted in-person in a private setting agreed upon in advance by participants and research staff. Interviews will be digitally audio recorded and transcribed for subsequent qualitative analysis. Respondents will be paid an incentive of \$30 for each interview. Interview guides will explore: (1) **Individual characteristics and circumstances.** We will ask people to tell us about themselves, their life circumstances (e.g., housing, employment or school, transportation, financial support), and their daily routine. We also will assess the impact of positive and negative life experiences on their injection drug use. The relationship of these factors to risk behavior will be explored. (2) **Family and other interpersonal relationships.** We will ask participants to tell us about their family and other significant interpersonal relationships they have, including the nature of the relationship, things they do together, and things they talk about. We will explore substance use and sexual risk behavior patterns within the participant's extended family and among significant others. (3) **Community contexts.** We will explore participant's perceptions of the

neighborhood(s) in which they live and socialize, including the types of people that live there, their social interaction patterns, and the places that people go to hang out and use drugs. We also will explore the availability and usage of social services, employment opportunities, and programs that promote community (e.g., churches). (4) **State policy.** We will ask about people's experiences with the legal system, including both incarcerated and non-incarcerated jurisdiction. We will explore the impact that involvement with the legal system has on their injection drug use. (5) **Sexual behavior.** We will explore participant's sexual behavior patterns, and the contexts or factors increasing or decreasing sexual risk likelihood. We also will assess participants' HIV/STD/hepatitis risk perceptions and concerns. Risk reduction behavioral and negotiation strategies will be explored. (6) **Substance use behavior.** We will explore participants' substance use patterns with a focus on injection drug use, and the contexts or factors increasing or decreasing use likelihood. We will assess (un)safe injection practices. We also will assess the saliency and centrality of substance use in participant's lives and the lives of their family and significant others.

A limited dataset of transcripts will be sent to the University of Washington DCC as part of the data harmonization project after the School of Medicine and Public Health's honest broker has reviewed them to assess PHI.

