A quantitative assessment of provider-level barriers will be conducted via a mail and email based survey among family medicine providers in WI in order to characterize barriers to optimal care and investigate opportunities to reduce health disparities among people who inject drugs (PWID). We will survey approximately 1,500 physicians specializing in family medicine who have a practice location in Wisconsin, as identified through an electronic database purchased from SK&A. To make specific comparisons among providers who have adopted office-based buprenorphine treatment (OBBT) in their primary care practice to those who have not, we will use a case-control study design, matching providers who have received a DEA waiver to prescribe buprenorphine to up to 2 non-waivered providers who practice in the same county. Cases have been identified through the Substance Abuse and Mental Health Services Administration's (SAMHSA) website. SAMHSA's database will be crosschecked by internet searches and phone confirmation to ensure that each provider is still practicing at reported location. We theorize that providers who have adopted office-based buprenorphine treatment have general awareness of the epidemic, and understanding barriers they face may be imperative. Controls (non DEA-waivered providers) will be drawn from the SK&A database. To achieve the target sample size of 1,500 providers, additional family medicine physicians will be sampled from the database, with priority given to providers practicing in the rural counties targeted in the parent study.

SSP clients will be recruited for individual-level interviews (Aim 2c) among participants who consent to participate in the client survey and seroprevalence study, described in Aim 1. Clients who participate in the cross-sectional study described above will be systematically invited (e.g., every nth person) to also participate in a qualitative interview. We anticipate conducting qualitative interviews with 5% of the cross-sectional sample (n=60) divided among the 6 counties. Additional interviews will be conducted if warranted by the data but a sample size of 30-50 is usually sufficient to achieve saturation and redundancy, a marker of sufficient sample size.

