## **Data analysis for Aim 2.**

Guided by principles of grounded theory, interviews will be analyzed for emergent themes as soon as interviews are transcribed. We will examine study transcripts to identify primary coding categories as well as a range of themes present within each category. Identified coding categories and themes will be organized into a formal code book, and we will extract illustrative quotes. Transcripts then will be formally content coded. If suggested by the data, thematic categories will be refined, merged, or subdivided, and/or new themes created. To ensure coding reliability, summaries will be coded by at least two raters who will discuss discrepancies and reach consensus. Decision trails will be noted and documented.

Quantitative data collected and returned via mail and email by rural primary care providers will be manually converted to an electronic format for data analysis. This data will be used to describe provider-level barriers, such as unawareness of the burden of HIV, HCV and sexually transmitted infections, a related tendency to under-screen for these conditions, and possibly stigmatizing attitudes towards people who inject drugs that may contribute to under-utilization of primary care services by high risk individuals. Insight gained through these surveys may be used for the design of the UH3 phase.

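### The provider survey is described as a survey of rural primary care providers, but it samples family physicians across Wisconsin and plans no rural subset

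*Combined protocol and SAP*

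**What the plan says.** Section 5.3 lists three goals for the Aim 2b provider mail and email survey. The first is "the willingness of rural primary care providers to provide treatment for HCV infection and/or opioid use disorder as primary prescribers". The second is "the prevalence and correlates of failure to provide appropriate screening for HIV, viral hepatitis, and sexually transmitted diseases for people who inject drugs", which has no rural qualifier. The third concerns "negative provider attitudes towards people who inject drugs that may serve as a barrier to effective primary care in rural communities", where rural communities are the setting.

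Section 6.0, Data analysis for Aim 2, names the source of the whole dataset: "Quantitative data collected and returned via mail and email by rural primary care providers will be manually converted to an electronic format for data analysis". It continues: "This data will be used to describe provider-level barriers, such as unawareness of the burden of HIV, HCV and sexually transmitted infections", and adds under-screening and possibly stigmatising attitudes.

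Section 4.0, Participant recruitment for Aim 2, describes another population. The exercise is a "survey among family medicine providers in WI in order to characterize barriers to optimal care", and the sample is stated as follows: "We will survey approximately 1,500 physicians specializing in family medicine who have a practice location in Wisconsin". It has three parts:

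- physicians holding a waiver to prescribe buprenorphine, found through a federal website, with no rural criterion;
- up to two non-waivered controls for each, from the same county, whatever that county is;
- further family physicians to bring the total to 1,500, with priority for the rural counties of the parent study.

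**The concern.** The population that the results will be said to describe is not the population sampled. Section 6.0 applies the rural label to every return, and no later step makes the label true.

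The study's own rationale makes it unsafe to assume that the difference is negligible. Section 1.3 says that rural areas commonly lack providers trained in HIV, viral hepatitis and addiction treatment. On that premise, waivered physicians may be found largely outside rural areas, their county-matched controls would come from the same places, and rural and non-rural physicians may answer differently.

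At stake are the reported levels of willingness, screening and attitudes. Section 6.0 says these may inform the UH3 design. The Triangulation of data text uses them as context when judging which counties suit implementation.

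**Working it through.** **Is there a rural filter anywhere?** The plan gives no power, precision, response rate or rural share for this survey, so there is no stated figure to reproduce. The check is of the text.

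| Place | Population or criterion |
|---|---|
| 5.3, goal 1 | rural primary care providers |
| 5.3, goal 2 | no rural qualifier |
| 5.3, goal 3 | barriers to care in rural communities |
| 6.0, analysis | all returns described as rural |
| 4.0, frame | family physicians, any Wisconsin practice location |
| 4.0, cases and controls | waiver status and county only |
| 4.0, top-up | priority for targeted counties, not restriction |
| 5.1, county status | Douglas and Brown, 2 of the 6 targeted counties, are not NCHS-rural |

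The priority rule covers only the top-up, does not exclude other areas, and favours some counties that are not NCHS-rural. The plan contains no rural eligibility rule for surveyed physicians, definition of rural practice, stratum, subset or weight.

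**Size of the error.** Let r be the rural share of respondents, and p_R and p_N the rural and non-rural proportions. The all-returns proportion is r × p_R + (1 − r) × p_N. Subtracting p_R gives:

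error = (1 − r) × (p_N − p_R)

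Neither factor is in the documents. Taking r from 20% to 70% and a difference of 5 to 20 points as assumptions, the error in percentage points is:

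| Rural share r | 5-point difference | 10-point | 20-point |
|---|---|---|---|
| 20% | 4.0 | 8.0 | 16.0 |
| 30% | 3.5 | 7.0 | 14.0 |
| 50% | 2.5 | 5.0 | 10.0 |
| 70% | 1.5 | 3.0 | 6.0 |

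For example, 0.3 × 5 = 1.5 and 0.8 × 20 = 16. With no difference, the error is zero.

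**Precision.** The 95% half-width for a proportion near 50% is 1.96 × √(0.25/n). A response of 30% to 60% is a further assumption and gives 450 to 900 returns.

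- All returns: 4.6 points (n = 450) to 3.3 points (n = 900).
- Rural only, fewest: 20% of 450 = 90, half-width 10.3 points.
- Rural only, most: 70% of 900 = 630, half-width 3.9 points.

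The error can therefore fall below the sampling uncertainty (1.5 against 3.3 to 4.6) or above it (16 against the same range). Unlike the half-width, it does not shrink with more returns.

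**The case against.** The best defence is that this is a labelling slip in a formative, descriptive survey. Section 4.0 says openly that the survey is of Wisconsin family physicians. A statewide search for waivered prescribers is reasonable if few practise in rural areas. Several parts of this defence stand.

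- **Pooling is not stated.** A reader might infer that the plan commits to one pooled estimate. Section 6.0 says only that the data will describe provider-level barriers. The fault is that a rural label is put on all returns and no breakdown is specified.
- **Not every goal is rural.** A reader might take all three goals to be about rural providers. Only goal 1 names them; goal 3 refers to the rural setting; the rural reading of goal 2 comes only from section 6.0.
- **The waiver comparison is largely unaffected.** Matching within county broadly balances county rurality between waivered and non-waivered physicians.
- **The sites do not hang on the survey.** A reader might infer that county selection is compromised. Section 3.0 and the Aim 3 recruitment text show the sites already chosen, on preliminary data, illness burden and familiarity with supportive stakeholders. The UH3 benchmarks do not name the survey, and no Aim 3 estimate uses it.
- **A rural subset may be imprecise.** In the least favourable case above (90 rural of 450, 5-point difference), the rural-only standard error is √(0.25/90) = 5.3 points. The all-returns figure has an error of 4.0 and a standard error of √(0.25/450) = 2.4, for a root mean square error of √(4.0² + 2.4²) = 4.7. It would on average lie slightly nearer the rural value, though with an interval centred in the wrong place. This argues for showing both figures, not for calling the full sample rural.

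The defence does not remove the conflict between section 4.0 and sections 5.3 and 6.0.

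**Conclusion.** The mismatch is real and lies in current text. Reporting all returns as those of rural primary care providers, as section 6.0 does, would attribute a partly non-rural sample's answers to rural providers. The harm is mainly to the descriptive estimates and their contextual use.

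The size is unknown. The range of about 1.5 to 16 points rests wholly on an assumed non-rural share of 30–80% and an assumed difference of 5–20 points. The documents do not give the number of waivered physicians, so the top-up could be a small or a large part of the 1,500. They therefore do not support a claim that the error must be large or must exceed sampling error.

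Weighting for waiver status would not cure this, since it would return a statewide figure rather than a rural one.

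**What to change.** **Preferred: report a rural estimate.**

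- Define rural practice by the ZIP code of the practice address, with one stated RUCA threshold. The client rule cannot be borrowed as it stands: section 4.0 requires a value above 4 and section 9.0 A a value of 4 or more. Both also admit residents of a syringe programme's catchment area; leave that clause out for providers.
- Estimate goals 1 and 3 among respondents with a rural practice address, and report non-rural physicians separately.
- Report goal 2 both overall and for rural practices.
- Keep the full-sample figure, labelled as Wisconsin family physicians.

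**Otherwise: correct the claim.** Replace the reference to rural primary care providers in sections 5.3 and 6.0 with Wisconsin family physicians, and drop the rural conclusion.

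**Cost.** The first option needs one derived variable and a further table. The frame is defined by practice location and the questionnaires are mailed, so addresses should be held. However, section 9.0 E says that the survey centre will not merge its sample files with the delivered data, so the centre would have to supply the rural indicator as a coded variable. The statistical cost is a wider interval: with 100 rural respondents the 95% half-width is 1.96 × √(0.25/100) = 9.8 points. The second option costs only wording, but gives up the rural question.

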#### 5.4 Data Collection for Aim 3 (Phase 2 - UH3)

**Prevention Navigation.** The health-related goals for PWID in the context of this study are multi-faceted, reflecting the heterogeneous needs of this vulnerable population. Accordingly, there is not a single, primary outcome which can be measured to evaluate the impact or effectiveness of the intervention. We therefore have proposed a study design that allows us to evaluate the influence of prevention navigation on progress toward a number of health goals. Because no single study design can account for all of the biases inherent in a non-randomized, multi-county intervention trial, we have proposed 2 different types of comparisons in our evaluation strategy (Appendix 1). Prevention Navigators will collect case notes and worksheets as part of the intervention, but this will only be accessible to them. These documents will be analyzed as data or shared with the UW-Madison research team.

The preferred method for intervention sessions is one-on-one in person, with optional one-on-one phone or video interventions when needed (ex: COVID-19 Pandemic). Staff will only contact the participant by their preferred method of contact, getting permission to leave messages before doing so. All virtual interventions and follow up calls will be performed on the navigators' cell phones or laptops provided by Vivent Health. Staff may also text participants to remind them of appointments, request a follow up call, or other short communication purposes. No messages will be sent without consent from the participant while filling out the locator form. Per Vivent Health policy, staff are permitted to communicate with clients about their care and treatment via Facebook messenger utilizing a professional Facebook account that is separate from any personal accounts. Staff are not permitted to use personal accounts to communicate with clients in a professional capacity. No data will be collected over social media accounts. Facebook conversations will not count as an intervention session.

**Survey and needs assessment.** The primary source of data collection in all three groups of the study will be from the ACASI questionnaire, administered at 0 months (baseline), 3 months, and 6 months from enrollment. All surveys will be administered on a tablet using the ACHESS application, by the participant accessing the survey in ACHESS on their smartphone or web browser on their own time, or over the phone. The data will be securely stored at UW-Madison and erased from the tablet if

applicable. The survey will consist of multiple choice questions designed to efficiently assess drug use history, access and utilization of prevention services, readiness for intervention, and injection related risk behaviors. The final survey a participant takes will include exit questions to help us evaluate and improve the program. Participants enrolled in the intervention between February 1, 2023 and March 31, 2023 will complete the baseline and 3 months ACASI questionnaire only.

**ACHESS.** All participants will complete study assessments using the ACHESS application. ACHESS can be accessed by downloading the application to a smartphone or via a web browser. Participants may also take part in optional non-research activities within the ACHESS app. These activities include: 1) posting on discussion boards, 2) utilizing the private message function to communicate with study staff or other participants, 3) viewing local community resources and their contact information, 4) viewing and saving motivational quotes of the day and logging thoughts of gratitude, and 5) accessing study staff contact information.

**Rapid testing for infectious diseases.** Upon enrollment, participants will provide 2 finger stick whole blood samples for rapid testing of HIV and HCV at baseline, 3-months, and 6-month follow up. Participants enrolled in the intervention between February 1, 2023 and March 31, 2023 will complete the baseline and 3-month rapid testing only. Vivent Health prevention staff are trained to perform point-of-care tests for these infections using the Alere Determine™ HIV-1/2 Ag/AB Combo (Alere Inc., Waltham, MA) and the OraQuick® HCV Rapid Antibody Test (OraSure Technologies, Bethlehem, PA). During the 20 minutes while awaiting test results, participants may complete the ACASI questionnaire (described above). If testing by appointment, participants should complete the survey before arriving to their appointment. If both rapid tests are non-reactive, then the study visit will end for non-intervention clients and an appointment will be made for their 3-month visit. Among intervention clients, the study visit will end and an appointment will be made for intervention visit or phone/video call. If either of the 2 rapid tests are reactive, then SSP staff will perform venipuncture to collect a blood specimen to be sent to the Wisconsin State Laboratory of Hygiene (WSLH) for confirmatory testing, and arrange a follow-up visit to review confirmatory test results and provide linkage to care, if needed. In the event that a participant cannot provide a blood specimen for confirmatory testing due to poor venous access, they will be invited to return at a later date for another blood draw attempt. Those confirmed to have active HIV or HCV infection will be linked to a local provider with the assistance of a Vivent Health case manager or Prevention Navigator.

The test results and risk data collected on the HCV and HIV test forms will be entered into Vivent Health's standard of practice database, ServicePoint. Study ID numbers will be included to identify the results as study participants. ServicePoint will securely send data to WEDSS regularly. Only those on the HCV team at WI DHS, which consists of three research team members, will have access to the data. Test forms will be securely faxed to UW-Madison and mailed to DHS, then securely locked at Vivent Health, UW-Madison, and DHS.

**Laboratory-based confirmatory testing and specimen handling.** Specimens received by WSLH will be processed for confirmatory testing per standard protocols (see Facilities and Resources for details). After completing the required testing and reporting test results to the testing agency and the WI Surveillance System, WSLH staff will store plasma specimens in preparation for shipping to the CDC and/or GHOST laboratories, as described in Section 5.2

**Collection of baseline demographic and risk behavior data.** Similar to Aim 1, we developed strategies to ensure that research activities are minimally-disruptive to the daily, core prevention activities of Vivent Health staff. Our pilot studies within SSPs have shown that this is essential for ensuring study protocol fidelity, maintaining high-quality data collection, and maximizing client willingness to participate. We will take advantage of existing data collection forms that are used

during HIV and HCV testing encounters to capture necessary individual-level data elements. All publicly-funded HIV testing sites in WI are required to use a uniform data collection and reporting system called Evaluation Web (Luther Consulting, LLC, Carmel, IN). Rapid HCV testing supported by WI DHS requires that agencies report client-level data using the Wisconsin Electronic Disease Surveillance System (WEDSS). With participant consent, the paper data collection forms used to capture the required demographic and risk behavior information will be transmitted to the UW-Madison based study coordinator via secure fax-to-PDF system, and will be stored on an encrypted server in a directory separate from other study data.

**Medicaid and Health Care Utilization Analysis.** We will link multiple existing datasets at the individual-level to evaluate the effects of the intervention health care use. These include the WI Department of Corrections (DOC) administrative dataset, Medicaid enrollment and claims data, WI State Laboratory of Hygiene (WSLH) HCV test records, WI Department of Health Services HCV Surveillance data, and the new county-level data resource developed through the activities under Aim 2a.

Based on our work with the JCOIN supplement, the UW-Institute for Research on Poverty (IRP) will assist in constructing the study dataset. The IRP has longstanding technical expertise in the construction and secure use of integrated person-level electronic datasets that combine State of Wisconsin administrative data including Department of Corrections and Medicaid administrative and health care claims data. Specifically, the IRP maintains the Multi-Sample Person File (MSPF) dataset which combines data for the universe of individuals interacting with several WI state agencies, including the Department of Health Services (home of the Medicaid program) and the Department of Corrections, at the person-level dating back to the late 1990's through the present. The MSPF is structured at the person-level, and each individual has a unique ID over time and across state agencies (e.g., a person who is incarcerated in a WI state prison and later enrolled in WI Medicaid) which supports longitudinal analysis.

For Aim 3, we will provide the UW IRP programming staff with our sample selection criteria. They will query the MSPF dataset with these criteria to identify possible linkages to our study participants along with a comparison group to evaluate the intervention itself. In addition to basic program participation information (e.g., dates of participation), the MSPF includes identifying variables for each unique person including Social Security number, date of birth, name, and the individual's identification number for each state agency that contributes to the MSPF in which s/he receives or has received services. The IRP will submit a finder file with the relevant identification information to each entity that is providing person-level data for the study. Upon receipt of these data, the IRP will then merge data from all sources at the person level, assign a unique, study number to each subject, and remove the personal identifying information used to match data across sources from the analytic dataset that is provided to the investigators.

The exchange of data between the IRP and state agencies is governed by the Data Use Agreements between the IRP and the respective agencies and follows a strict data security protocol to protect the confidentiality of individuals. The DUA between the IRP and the WI Medicaid program was modified and approved for this study in September 2018.

**COVID-19 Pilot Intervention.** All data will be collected in REDCap, ServicePoint, Vivent Health's secure server, or on a secure server only accessed by UW research staff. Sessions will happen via phone or Microsoft teams, Vivent Health's approved secure video call resource.

**Screening data** and locator forms will be stored on the Vivent Health server or secure PHI box and entered into REDCap for analysis by UW staff.

**COVID-19 Pilot Navigation** Participants will undergo a risk and needs assessment during the first

and last session of the intervention, as well as 30 days after Vivent returns to their full service model (if deemed appropriate post pandemic). The assessment will ask a shortened version of ACASI survey questions specifically relevant to the pandemic. The rest of the assessment will follow the same risk and needs outline as designed for UH3, just with goals specific to the pandemic. Data will be stored on the Vivent Health secure server before being uploaded to a PHI box for analysis. All participant data will be collected by the prevention navigators on their Vivent Health provided devices.

**At home testing** data will be collected online using Vivent Health's testing protocol. Testing forms will be filled out online, and collected by SSP staff. Individual data will be uploaded to the PHI box, REDCap, or Vivent Health server by the prevention navigators.

**Data Matching** We will combine data for participants who completed both Phase 1 and Phase 2 of the study. Combining information across studies could potentially increase the value of individual's participation beyond what is learned in any individual study and increase knowledge about health problems that can result from injecting drugs and ways to reduce the risk of HIV, hepatitis C, and overdose.

